**LIST OF ABBREVIATIONS**

GCP	Good Clinical Practice
SMF	Study Master File
SOP	Standard Operating Procedure
CNORIS	Clinical Negligence and Other Risks Scheme
AP	Anterior-posterior

## INTRODUCTION

### 1.1 BACKGROUND

Exposure to ionising radiation is understood to be associated with a small increase in the risk of developing cancer later in life. Therefore, all medical exposures need to be justified to ensure that the benefits from the exposure outweigh the risk, and optimised to ensure that the exposure is as low as reasonably practicable consistent with the intended purpose of the exposure.

Patient dose audit is an important part of the optimisation process. It gives information as to the level of dose received on average for an examination on one x-ray machine, allowing a comparison between multiple x-ray machines on the same site and between sites. For all commonly undertaken examinations, national reference levels exist; these are created from local data from all over the UK. Any institution is able to compare their local performance against these national values and determine if they are in line with average national performance or if urgent optimisation is required.

Whereas a patient dose audit for adult x-ray examinations requires only limited information relating to the exposure factors used and the amount of radiation measured by the equipment as delivered to the patient, the method for paediatric patient dose audit also requires a measurement of patient size to be made. This measurement should be either the anterior-posterior or lateral depth of the patient, depending on the examination projection.

Alternatively, a measurement of height and weight can be made, from which can be estimated the equivalent cylindrical diameter of the patient, which is equivalent to the measured depth.

National data collection exercises have revealed that these measurements are not being routinely made for paediatric patients undergoing x-ray examinations however. This has meant that no national reference levels have been proposed for paediatric x-rays since 2000. Since 2000, there have been significant technological improvements to the equipment used for x-ray imaging throughout the UK, so these reference values are out of date.

The lack of up to date reference values is affecting efforts to optimise paediatric x-ray exposures across the UK, despite this being the patient cohort for whom optimisation is most important.

### 1.2 RATIONALE FOR STUDY

A non-commercial computational model has been developed in-house to estimate the patient's anterior-posterior or lateral depth using the radiographic image and the known exposure factors with which it was undertaken. This model has been tested using single composition phantoms and found to be accurate. If it was found to be accurate for real clinical examinations, this would automate the measurement of patient size and give local institutions the additional estimate of patient size required for local patient dose audit. In turn, this would provide the national data required to propose national reference values for paediatric x-ray examinations, which would give all local institutions an important comparator for their performance. This would lead to optimisation in those sites most requiring it; nationally, paediatric x-ray imaging would improve in time.

This pilot study is necessary to determine if the computational model is accurate enough to be relied upon.

## 2. STUDY OBJECTIVES

### 2.1 OBJECTIVES

#### 2.1.1 Primary Objective

To determine how accurate the computational model is at determining the patient's anterior-posterior abdomen depth using the radiographic image and the known exposure factors with which it was acquired. Accuracy will be determined by comparing this result with an actual measurement of the patient's anterior-posterior abdomen depth made at the time of the examination.

## **2.1.2 Secondary Objectives**

Any systematic inaccuracy found in the study could be used to further improve the values used in the computational model.

## **2.2 OUTCOMES**

### **2.2.1 Primary Outcomes**

A measure of the accuracy with which the computational model estimates the anterior-posterior depth of patients undergoing abdominal x-ray examinations.

### **2.2.2 Secondary Outcomes**

Any identified systematic inaccuracy could be used to further improve the values used in the computational model.

## **3. STUDY DESIGN**

### **3.1 STUDY DESCRIPTION**

Willing volunteers will be found from patients who have been referred for an AP abdomen x-ray examination in the Radiology department at Ninewells Hospital. Any patient suffering severe abdominal pain when attending for the examination will be excluded as it will be necessary for light physical contact to be made with the patient's abdomen. Any patient that has had an injection of contrast media within the previous 24 hours will be excluded from the study as the computational model is not equipped to work with the presence of contrast media at present.

When the patient reports to main reception, if their attendance is for an AP abdomen x-ray the receptionist will give them the PIS and a reply slip saying that if they wish to take part in the study after having read the PIS they should inform the receptionist. The receptionist will then contact the PI who will be in the radiology department.

When it is time for the volunteer's examination, a radiographer will collect them from the waiting area as normal and bring them to the x-ray room as normal. Their examination will be performed on the Fuji Digital Radiography mobile x-ray machine in room D of main radiology at Ninewells Hospital.

Each patient will be assigned a unique numerical study ID that will be used to correlate the measurement of their anterior-posterior depth with their anonymised image.

The patient will lie on the x-ray couch in room D in the examination position, as directed by the radiographic staff. A measurement of the patient's AP abdomen depth will be made using a device that will attach to the side of the x-ray couch. This device is non-commercial and made in-house. It is not CE marked. Physical contact with the patient will be minimal; a wooden bar will rest gently on their abdomen. This will allow the AP abdomen depth to be read on the scale that is affixed to the x-ray couch.

This measurement will be recorded alongside the clinical indication for the patient under an anonymous and unique participant ID on a patient study form.

The AP abdominal x-ray examination will be undertaken by radiographic staff in accordance with local protocol and with no influence from this study. On completion, the patient's x-ray image will be transferred to PACS as normal, where it will be available for radiologist reporting. The patient will leave the department as normal with no additional request made of them for this study.

[figure not shown]
The anonymised patient's x-ray image will be removed directly from the x-ray equipment using an NHS password protected USB memory stick. During this transfer, the software on the x-ray equipment will anonymise the image. This process has been checked using test

patients – the anonymisation process is complete – no patient identifiable information will be left on the image or within the electronic header.

The image will be transferred from the USB memory stick to an NHS Tayside password protected computer. From there, the necessary measurements will be made to allow the computational model to be used to estimate the patient's AP abdomen depth. This estimate will be compared to the physical measurement of AP abdomen depth made for the corresponding patient as recorded on the patient study form – this will determine the accuracy of the estimate.

There is no need for any patient follow up. Individual patients will only participate in the trial once. As this is a pilot study, 20 patients will be recruited in total. This will be enough as an initial cohort to determine whether the computational model is accurate enough to merit further clinical investigation, or if it is in need of adjustment.

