## **8. STATISTICS AND DATA ANALYSIS**

### **8.1 SAMPLE SIZE CALCULATION**

The sample size for this pilot study will be 20 patients. There is no statistical aim or calculation in deriving this number; 20 is simply a high enough number as to allow for confidence in the computational model where all or most results are found to be individually accurate.

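### The reference depth is a single reading on an in-house device with no repeat or accuracy check described, so device error would be counted as model error

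*Combined protocol and SAP*

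**What the plan says.** All references are to the combined protocol and SAP.

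- **Reference standard.** The primary objective (2.1.1) assesses accuracy by "comparing this result with an actual measurement of the patient's anterior-posterior abdomen depth made at the time of the examination". Section 3.1 repeats this: "This estimate will be compared to the physical measurement of AP abdomen depth made for the corresponding patient".
- **Device.** Section 3.1 states: "This device is non-commercial and made in-house". It adds that the device is not CE marked. It attaches to the couch, and "a wooden bar will rest gently on their abdomen" while the depth is read from a scale. The patient lies in the examination position.
- **Number of readings.** Section 3.1 speaks of one measurement. Section 7.1 lists three recorded variables: sex, clinical indication and a depth.
- **Analysis.** Section 8.2 expresses predicted against measured depth as a percentage difference per patient. It summarises these by average, median, minimum and maximum, and adds a t-test. It has no term for error in the measured depth.
- **Use of the result.** Section 2.1.2 says "Any systematic inaccuracy found in the study could be used to further improve the values used in the computational model", and 2.2.2 says much the same.
- **Prior checks.** Of the model, section 1.2 says "This model has been tested using single composition phantoms and found to be accurate". There is no matching statement about the depth device.
- **Sample size.** Section 8.1: "The sample size for this pilot study will be 20 patients", and "There is no statistical aim or calculation in deriving this number".

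**The concern.** The primary outcome is a difference between two quantities, each with its own error, but the plan assigns the whole difference to one of them. With one reading per patient, the 20 differences cannot be split into model error and reading error.

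The two parts of reading error act differently. A constant device offset moves the mean difference, looks like model bias, and is the part that could be carried into the model under 2.1.2 and 2.2.2. Random reading error leaves the mean alone on average but widens the spread and stretches the minimum and maximum deviations. It also counts against the 8.1 expectation that all or most results will be individually accurate.

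The pilot exists to say whether the model merits further clinical investigation or needs adjustment (3.1 and 4.1). An unquantified reference error bears directly on that choice.

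**Working it through.** **The plan's own figure.** The only figure is 20 patients. Section 8.1 says it was not calculated, so there is nothing to reproduce.

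**Inputs.** From the documents: n = 20, one reading each, percentage differences. Assumed, because the documents give no value: depth 22 cm; single-reading SD 0.2, 0.5 or 1.0 cm; true model-error SD 5% or 3% of depth; independent errors; two-sided 5% level for the t-test.

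**Decomposition**, taking the difference as predicted minus measured:

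- observed bias = model bias − device bias
- observed SD = √(model SD² + reading SD²/k), for k independent readings averaged
- limits of agreement = ±1.96 × SD about the mean difference

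**Random error.** Reading SD as a percentage of depth: 0.2/22 = 0.91%, 0.5/22 = 2.27%, 1.0/22 = 4.55%. Worked example, model SD 5% and reading SD 0.5 cm: √(5² + 2.27²) = 5.49%, and 1.96 × 5.49 = ±10.8%. Share of variance due to reading error: 2.27²/5.49² = 17%.

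| Model SD | True limits | Reading SD | Apparent limits, one reading | Reading error share of variance | Limits, mean of two independent readings |
|---|---|---|---|---|---|
| 5% | ±9.8% | 0.2 cm | ±10.0% | 3% | ±9.9% |
| 5% | ±9.8% | 0.5 cm | ±10.8% | 17% | ±10.3% |
| 5% | ±9.8% | 1.0 cm | ±13.2% | 45% | ±11.7% |
| 3% | ±5.9% | 0.2 cm | ±6.1% | 8% | ±6.0% |
| 3% | ±5.9% | 0.5 cm | ±7.4% | 36% | ±6.7% |
| 3% | ±5.9% | 1.0 cm | ±10.7% | 70% | ±8.6% |

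**Constant offset.** An offset of 0.5 cm is 0.5/22 = 2.3% of depth, and averaging repeats does not reduce it. If the model is truly unbiased, the paired t-test on 20 patients has noncentrality (2.27/SD) × √20. That is 3.39 if the observed SD of differences is 3%, and 2.03 if it is 5%. The probability of a significant result, which would be read as model bias, is about 0.89 and 0.49 respectively.

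**What duplicates would estimate.** The within-patient SD is √(Σd²/2n), where d is the difference between a patient's two readings. Twenty pairs give 20 degrees of freedom, so the 95% confidence interval runs from 0.77 to 1.44 times the estimate.

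**The case against.** The strongest reply is that the documents are silent, not negative. A reader might infer that the device was never checked. The text does not support that: it describes no check, but does not say none was made, and one figure in section 3.1 was not available for this review. Nor is the measurement wholly uncontrolled, since the patient lies in the examination position. Level, contact pressure and breathing state are what remain open, and leaving these unstated is closer to missing detail than to a wrong method.

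A reader might also infer that device error will be built into the model. Sections 2.1.2 and 2.2.2 are permissive, prescribe no refit and do not say how values would be adjusted. Only the systematic part could carry over.

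On size, every SD above is assumed. If the bar reads to within an SD of 0.2 cm, reading error is only 3% to 8% of the variance and hardly matters. The 70% figure pairs the worst reading SD with the best model SD. With 20 patients an SD is itself known only to about 0.76 to 1.46 times its estimate, so apparent limits of ±10.8% are compatible with roughly ±8.2% to ±15.7%. Duplicates shift the limits by less than that in every row of the table. Because the plan sets no accuracy limit, no particular shift can be shown to reverse the decision, and that decision is only whether to go on or adjust.

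The remedy has limits too. Two readings by one operator with one bar share errors of level, compression and technique, and a check on rigid objects tests the scale but not soft tissue.

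All of this stands as a restraint on wording and size. It does not remove the core: as written, the plan gives the study no way to tell reference error from model error.

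**Conclusion.** The point holds as a cheap improvement. One reading per patient on an in-house device, with no repeat and no check against known thicknesses described, means that a device offset would be read as model bias and random reading error as model imprecision.

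The documents do not fix the size. At a 22 cm depth with a reading SD of 0.2 to 1.0 cm, the distortion runs from negligible (±9.8% seen as ±10.0%) to substantial (±5.9% seen as ±10.7%), with reading error between 3% and 70% of the observed variance. A 0.5 cm offset would appear as about 2.3% bias. These are illustrations under assumed values, not estimates for this device. The width of that range is itself the reason to measure the reading error.

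The documents do not support concluding that the device is inaccurate, or that the pilot's decision will be wrong.

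**What to change.** **In section 3.1:**

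- After the first reading, lift and reposition the bar and take a second reading without reference to the first. Record both and use their mean as the reference depth.
- Before the first patient, read objects of known thickness with the device, then report or correct its offset. If this has already been done, report the result.
- Take the readings at the level of the image region the model uses, leaving the exposure unchanged.

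**In section 7.1:** add a field for the second reading.

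**In section 8.2:** report the within-patient SD of the duplicates beside the model differences. Call it a lower bound on reference error, because duplicates do not reveal errors common to both readings, such as compression, level or operator. State that model values will not be adjusted for any bias that the device check explains.

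**Cost.** Slightly longer bar contact, one extra form field, a short bench check, and a protocol amendment with the approvals listed in 11.1. No additional patients, staff or radiation are needed.

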### 4. STUDY POPULATION

#### 4.1 NUMBER OF PARTICIPANTS

As this is a pilot study, 20 patients will be required after any drop outs. This will be enough as an initial cohort to determine whether the computational model is accurate enough to merit

further clinical investigation, or if it is in need of adjustment. It would be prudent to aim for an even male/female split.

As there is no patient follow-up, the patient's trial recruitment ends when they leave the Radiology department having had their abdomen x-ray examination.

If any participant chooses to withdraw from the study after their x-ray examination, their data will be deleted from the study database. These participants will be replaced to ensure 20 participants overall.

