## **7. DATA COLLECTION & MANAGEMENT**

### **7.1 DATA COLLECTION**

The patient's sex and clinical indication (i.e. the reason given for the AP abdomen x-ray examination on the request) will be recorded along with the physical measurement of their AP abdomen depth.

These 3 variables will be recorded at the time of the x-ray examination by the principal investigator on the patient study form. The patient's x-ray image will be taken directly from the x-ray equipment by the principal investigator; the image is anonymised during this transfer process.

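### No masking or locking is described for the image measurements, so any judgement in them could bias the accuracy result in the model's favour

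*Combined protocol and SAP*

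**What the plan says.** Section 3.1 describes the depth measurement first. The patient lies on the couch and a bar is rested on the abdomen: "This will allow the AP abdomen depth to be read on the scale that is affixed to the x-ray couch". The x-ray follows, and it "will be undertaken by radiographic staff in accordance with local protocol and with no influence from this study". The image is then anonymised, exported and moved to a hospital computer, where "the necessary measurements will be made to allow the computational model to be used to estimate" the depth. Next, "This estimate will be compared to the physical measurement of AP abdomen depth made for the corresponding patient".

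Each patient receives "a unique numerical study ID that will be used to correlate the measurement of their anterior-posterior depth with their anonymised image".

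On roles, section 7.1 says of sex, clinical indication and measured depth: "These 3 variables will be recorded at the time of the x-ray examination by the principal investigator on the patient study form". The same section has the PI take the image from the equipment, and section 8.2 assigns all analyses to the PI. Section 3.1 does not say who makes the measurements on the image.

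Section 8.2 expresses the result as a percentage difference for each patient, summarised by average, median, minimum and maximum. Section 8.1 ties confidence in the model to most or all of the 20 results being accurate one by one, without setting a limit. The stated use of the result is to "determine whether the computational model is accurate enough to merit further clinical investigation, or if it is in need of adjustment"; section 4.1 repeats this.

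**The concern.** The study asks one question: how close is the model's estimate to the measured depth? The answer is a fair test only if the estimate is produced without reference to the depth it will be judged against. Here the depth exists first, and the person who records it also handles the image and runs the analysis. The step between, measuring on the image, has no named reader, no described masking and no point at which the estimates become final.

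If that step leaves room for choice, a reader who knows the depth may settle, without intending to, on values that bring the estimate closer to it. Estimates could also be revisited once a large discrepancy is seen. Either would make the model look more accurate than it is. The decision at stake is whether to take the model forward or to adjust it.

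**Working it through.** There is no planned figure to reproduce: section 8.1 states that the 20 was not calculated. The check is of sequence, roles and safeguards.

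**1. Sequence and roles**

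| Step | Who | Section |
|---|---|---|
| Depth read on the couch and recorded | PI records | 3.1, 7.1 |
| X-ray taken | Radiographic staff | 3.1 |
| Image taken from the equipment | PI | 7.1 |
| Measurements made on the image, model run | Not stated | 3.1 |
| Estimate compared with depth | PI, as part of all analyses | 3.1, 8.2 |

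Section 8.3 adds that data are entered electronically soon after they are acquired. The depth is therefore likely to be on file when the image is measured. Whether images are measured one by one or together is not stated.

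**2. Provisions that might close the gap**

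- Anonymisation (3.1) removes patient identity. It does not hide the depth, since the study ID exists to join image and depth.
- Database lock (7.2) is given by reference to an SOP. Nothing there says that estimates are fixed before the depths are linked.
- The steering and data monitoring committees (9.3, 9.4) are given general oversight only.
- The flowchart in 3.2 and the cited SOPs could not be read, so the finding is limited to the readable text.

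**3. What is already protected**

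- The reference depth is read before the image exists, so the estimate cannot influence it.
- The exposure factors, which section 1.2 names as model inputs, come from an examination that the study does not influence.

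That leaves the measurements made on the image.

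**4. Direction of any bias**

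Let M be the measured depth and P the estimate. Section 8.2 does not name the denominator; take it as M. Then D = 100 × (P − M) / M.

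M is already fixed. Suppose knowledge of M draws the estimate a fraction w of the way towards it, with w from 0 to below 1. The estimate becomes P + w(M − P), and the difference becomes

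100 × [P + w(M − P) − M] / M = 100 × (1 − w)(P − M) / M = (1 − w)D.

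Every non-zero difference shrinks in absolute size when w is above 0. For any fixed limit of accuracy, the number of patients within it can then only stay the same or rise. If the measurements follow a rule that leaves no choice, w = 0 and nothing changes.

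**5. Size**

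A numerical answer needs w, the spread of the differences and the limit that counts as accurate. The documents give none of these, so no magnitude is offered.

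**The case against.** The strongest reply is that the mechanism is unproven. Bias needs a reader who knows the depth and measurements that allow discretion, and the documents establish neither. Section 1.2 describes a model that works from the image and known exposure factors, and looks forward to automating size measurement. This stands, and it is why the point is conditional. It does not remove the point: automation is what section 1.2 hopes an accurate model would bring, whereas section 3.1 has measurements made on each image and gives no rule for them.

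Second, this is a small pilot. A falsely favourable result would lead to further testing, not directly to clinical use. That also stands and limits the weight of the point. But choosing between further investigation and adjustment is the pilot's purpose, and that choice is what would be affected.

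Third, locking by a PI who recorded the depths prevents later revision but not recall while measuring. This is correct, and the report should acknowledge it.

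Three stronger readings are tempting but not supported:

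- A reader might infer that the PI makes the image measurements. Sections 7.1 and 8.2 make this probable; no section says so.
- A reader might infer that the model could be tuned to these patients before the primary result is taken. Sections 2.1.2 and 2.2.2 speak of inaccuracy already found, and section 3.1 puts estimate before comparison, so adjustment most naturally comes afterwards. All that is missing is an explicit statement that the primary result uses the unadjusted model.
- A reader might infer a definite gain in the number of accurate results. Any such figure would rest wholly on assumed inputs.

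**Conclusion.** The point holds in conditional form. No readable section keeps the person measuring the images unaware of the depth, or saves the estimates before they are compared. If the image measurements involve any judgement, the per-patient percentage differences, and the judgement that most or all are accurate, are open to bias in the model's favour. This shows exposure to bias, not that bias will occur. The size cannot be estimated from the documents and may be nil.

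The conclusion assumes that the reader has access to the depths, which is likely but unstated, and that the unreadable flowchart and SOPs contain no relevant safeguard. It is a cheap improvement, worth making because the safeguard cannot be recreated once estimates and depths have been seen together.

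**What to change.** Amend sections 3.1 and 8.2 to say that:

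1. The image-measurement procedure is written down and the model values are fixed before the first participant, and the person who makes the image measurements is named by role.
2. All image measurements are made by study ID in one batch, without the study forms or the depth file to hand.
3. The estimates are date-locked before they are linked to the measured depths.
4. The primary result uses only the locked estimates. Any later adjusted model is reported separately and labelled as fitted to the same patients.
5. If the PI makes the measurements, the report states that the safeguard is locking, with recall still possible, and not full masking.

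This version needs no extra patients or staff. Full masking would need a reader who has not seen the depths; the management group in section 9.1 consists only of the chief investigator and the PI, so that may need another person. The downside is that results are seen later, and a short amendment needs approval from the Sponsor, the REC and the R&D office under section 11.1.
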